9.3. Vital Signs

Descriptive summaries of actual values and changes from baseline will be calculated for seated systolic blood pressure, standing systolic blood pressure, and supine systolic blood pressure, seated diastolic blood pressure, standing diastolic blood pressure, and supine diastolic blood pressure, heart rate, respiration rate, and body temperature. These summaries will be presented by visit and treatment group. Vital signs are collected at all study visits. During the infusion periods (Visit 3-Visit 7 and Visit 11- Visit 15), orthostatic vital signs (supine systolic and supine diastolic blood pressure compared to standing systolic and standing diastolic blood pressure) should be measured prior to infusion start and at approximately [REDACTED] after infusion start. Seated systolic and seated diastolic blood pressure is measured at multiple timepoints during and after each infusion. Abnormal vital sign values will be flagged in the listings. Abnormal vital sign values are as follows:

- Seated systolic blood pressure value < 90 mmHg
- Seated systolic blood pressure value > 180 mmHg
- Seated diastolic blood pressure value < 50 mmHg
- Seated diastolic blood pressure value > 110 mmHg
- Incidence of orthostatic hypotension (a decrease in systolic blood pressure of > 20 mm Hg and/or a decrease in diastolic blood pressure of > 10 mm Hg between supine and standing)
- Heart rate > 100 beats per minute
- Temperature > 37.5°C
- Temperature < 36.5°C
- Respiration rate > 20 breaths per minute
- Respiration rate < 12 breaths per minute

The vital sign measurements that meet the criteria for blood pressures of special interest (listed below) will also be identified from the vital signs source data and summarized separately by study visit, timepoint, and treatment.

- Seated systolic blood pressure >180 mmHg
- Seated systolic blood pressure > 200 mmHg
- Seated systolic blood pressure < 90 mmHg
- Seated diastolic blood pressure > 110 mmHg
- Seated diastolic blood pressure > 120 mmHg
- Seated diastolic blood pressure < 50 mmHg
- A change of $\geq 30\%$ from baseline in seated systolic and/or seated diastolic blood pressure

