10.4.4 ANALYSIS OF THE SECONDARY SAFETY ENDPOINTS

Actual values and changes from baseline in clinical laboratory measurements, vital signs, body weight, and S-STS scores will also be assessed and summarized. Abnormal lab or vital sign values will be determined and flagged in the listings. Laboratory shift tables or graphics displaying the change (number of subjects) relative to the reference range from baseline to each study visit may also be presented for each test. The investigator should exercise his or her medical and scientific judgment in deciding and documenting whether an abnormal laboratory finding, or other abnormal assessment is clinically significant.

For secondary safety endpoints that are continuous in nature (e.g. clinical laboratory parameters, systolic and diastolic BP, heart rate, respiratory rate, body temperature, body weight, S-STS score) the mean, median, minimum, maximum, and standard deviation will be plotted over time.

For secondary safety endpoints that are categorical in nature (e.g. physical exam or ECG abnormalities), the frequency counts and percentages will be presented as a descriptive summary.

Per-subject extent of exposure will be listed.

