6. MONITORING FOR ADVERSE REACTIONS

Throughout the infusion, the blinded Outcomes Assessor or designee should continuously assess the subject for signs of AEs.

In the event of an AE, the PI or designee physician should be notified, and the event should be recorded for later transcription into the CRF. The PI should assess immediately whether an AE is an AE of special interest and/or an SAE and report it accordingly, as per the protocol.

Table 3. Recommended AE Actions for PI or Physician Designee

Mild Events	

 • Body temperature >38.0°C (>100.4°F) but <39.0°C (<102.2° F) • Chills • Dizziness • Fatigue • Flushing • Mild-to-moderate itching • Redness of skin or rash • Urticaria (hives) in the absence of any other sign of symptom • Nausea / Vomiting 	
Stop the infusion, recheck vital signs, and notify the PI or physician designee. After assessment by a physician and consideration of treatment of fever with acetaminophen (if applicable), the unblinded Infusion Nurse may restart the infusion rate at half the rate at the onset of the infusion event and maintain the reduced rate for at least 30 minutes. If this rate is tolerated, the unblinded Infusion Nurse may increase the rate as tolerated by 30 mL per hour (0.5 mL/min) every 30 minutes (± 5 minutes) as tolerated.

Moderate to Severe Events	

 • Bronchospasm (wheezing, coughing) • Hoarseness or other signs of laryngeal edema • Throat or mouth pain or irritation • Chest pain/back pain • Shortness of breath • Fever ≥39 °C (102.2° F) • Rigors • Hemoglobinuria • Oliguria • Sustained hypertension (systolic BP (SBP) >170 and/or diastolic BP (DBP) >100 not present before the first infusion) • Sustained hypotension (SBP <90 and/or DBP <50 not present before the first infusion) • Tachycardia (HR>100 bpm) • Signs / symptoms of volume overload 	
Stop the infusion, recheck vital signs, and notify the PI or physician designee. The PI or physician designee should administer appropriate supportive treatment, as necessary. The infusion should not be restarted, and the subject should not be dosed further. Notify the Medical Monitor(s) as soon as possible (preferably by end of business day).

Life-Threatening Events	

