		XXXXXX	DDMMYYYY (X)	XX.X	XX	XX		XXX	

Abbreviation: ND = not done.
 Note: Study day is calculated relative to the date of first dose. Abnormal vital signs are as follows: Heart rate > 100 beats per minute, Temperature > 37.5°C or < 36.5°C, Respiration rate > 20 breaths per minute or < 12 breaths per minute.
 [1] Treatment is based on treatment received.

Programming Note: if a measurement is abnormal, place an asterisk (*) next to the value in the cell.

Listing 16.2.8.2.2
Blood Pressure
All Subjects

Subject ID	Treatment [1]	Study Visit	Date of Assessment (Study Day)	Standing Blood Pressure (mmHg)		Supine Blood Pressure (mmHg)		Sitting Blood Pressure (mmHg)		Abnormal?	BPSI?
				Systolic	Diastolic	Systolic	Diastolic	Systolic	Diastolic		
XXXXXX	XXXXXX	XXXXXX	DDMMYYYY (X)	XXX	XX	XXX	XX	XXX	XX	XXX	XXX
		XXXXXX	DDMMYYYY (X)	XXX	XX	XXX	XX	XXX	XX		
		XXXXXX	DDMMYYYY (X)	XXX	XX	XXX	XX	XXX	XX		
		XXXXXX	DDMMYYYY (X)	ND	ND	ND	ND	ND	ND		
		XXXXXX	DDMMYYYY (X)	XXX	XX	XXX	XX	XXX	XX		

Abbreviation: BPSI = blood pressure of special interest, ND = not done.

Note: Study day is calculated relative to the date of first dose. Abnormal blood pressure vital signs are as follows: seated systolic blood pressure < 90 mmHg or > 180 mmHg, seated diastolic blood pressure < 50 mmHg or > 110 mmHg, or incidence of orthostatic hypotension (a decrease in systolic blood pressure of > 20 mm Hg and/or a decrease in diastolic blood pressure of > 10 mm Hg between supine and standing). BPSIs are as follows: seated systolic blood pressure > 180 mmHg, seated systolic blood pressure > 200 mmHg, seated systolic blood pressure < 90 mmHg, seated diastolic blood pressure > 110 mmHg, seated diastolic blood pressure > 120 mmHg, seated diastolic blood pressure < 50 mmHg, or a change of $\geq 30\%$ from baseline in seated systolic and/or seated diastolic blood pressure.

[1] Treatment is based on treatment received.

Programming Note: If a measurement is abnormal, place an asterisk (*) next to the value in the cell.

Statistical Analysis Plan,
 Sponsor Alkermes, Inc.
 Protocol Number ALK6021-201
 PCN Number ALKA7951

Listing 16.2.8.3
 12-Lead Electrocardiogram (ECG) Results
 All Subjects

Subject ID	Treatment [1]	Was ECG Performed?	Date/Time of ECG (Study Day)	Overall Interpretation	Heart Rate (bpm)	QT Interval (msec)	QTcF Interval (msec)
XXXXXX	XXXXXX	XXX	DDMMYYYY/HH:MM (XX)	XXXXXXXX	XXX	XXX	XXX
		XX	DDMMYYYY/HH:MM (XX)	XXXXXXXXXXXX	XXX	XXX	XXX
		XXX	DDMMYYYY/HH:MM (XX)	XXXXXXXXXXXX	XXX	XXX	XXX

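### SAP 9.3's temperature flag is listing-only and differs from the infusion manual's event tiers, so measured fever or tachycardia not reported as an AE is never counted by arm

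*SAP*

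**What the plan says.** SAP 9.3 lists the limits for abnormal vital signs. For temperature they are "Temperature > 37.5°C" and "Temperature < 36.5°C"; for heart rate the limit is above 100 beats per minute. Their stated use is "Abnormal vital sign values will be flagged in the listings". The footnote to Listing 16.2.8.2.1 (SAP 14.3) repeats them: "Heart rate > 100 beats per minute, Temperature > 37.5°C or < 36.5°C". Its programming note says "if a measurement is abnormal, place an asterisk (*) next to the value in the cell", so low and high temperatures get the same mark. The listing shell has visit and date columns but no timepoint column.

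Temperature and heart rate are tabulated in Table 14.3.6.1.1, which reuses the laboratory shell: n, mean, SD, median, minimum and maximum by visit and arm. Only seated blood pressure has a table that counts subjects beyond a limit by arm (Table 14.3.6.1.2, blood pressures of special interest).

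Protocol Appendix 11, section 6, Table 3 uses other temperature limits. Its mild events include "Body temperature >38.0°C (>100.4°F) but <39.0°C (<102.2° F"). Its moderate to severe events include fever of 39°C or more and heart rate above 100 bpm. The SAP uses neither temperature tier.

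**The concern.** The trial's primary question is the safety of a plasma-protein infusion, and the infusion manual names fever and tachycardia among the signs staff must act on. The SAP's only rule for an abnormal temperature spans a band of 37.5 − 36.5 = 1.0°C, is applied to many readings per subject, and treats low and high values alike. If ordinary variation trips it in most subjects, the asterisks say little about reactions. And because the mark appears only in a listing, it gives no comparison between arms.

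The adverse event tables fill part of the gap. Under Protocol 8.1.1, though, an abnormal assessment is an adverse event only if it is a clinically significant finding. The sponsor saw this limit for blood pressure: Protocol 8.4.3 has values that meet the limits but are not judged adverse events analysed separately, and SAP 9.3 tabulates blood pressures of special interest by visit, timepoint and arm. Temperature and heart rate have no such table.

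**Working it through.** **The plan's own figure.** The documents state no expected rate for the temperature flag. The only quantitative safety-signal figure is the upper bound of about 5% for an unobserved event in 60 active subjects (Protocol 10.5, SAP 3.2). It reproduces: 3/60 = 5.0%; the exact one-sided bound is 1 − 0.05^(1/60) = 4.87%.

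**Readings per subject.** Appendix 11, sections 5.3 and 5.4, require temperature before the infusion (1), every 15 minutes in the first hour (4), then every 30 minutes to the end, and every 30 minutes for 4 hours afterwards (8). Infusion duration is redacted. Assuming 1 hour:

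- per infusion day: 1 + 4 + 8 = 13
- ten infusions: 13 × 10 = 130
- other visits: 19 − 10 = 9, one reading each, since "Vital signs are collected at all study visits"
- total: 130 + 9 = 139 (159 for a 2-hour infusion, 179 for 3 hours)

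**How little it takes.** With independent readings, a per-reading flag rate p marks 95% of subjects when 1 − (1 − p)^139 = 0.95, so p = 1 − 0.05^(1/139) = 2.1%. With one reading per visit (19), p = 14.6%.

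**Simulated flag rate with no drug effect and no fever.** Assumptions, none from the documents: normal random-intercept model, values rounded to 0.1°C, total SD 0.25 to 0.45°C, within-subject correlation 0.3 to 0.7, 4,000 subjects per scenario.

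| Assumed mean | Readings flagged | Subjects with any flag, 139 readings | Subjects with any flag, 19 readings |
|---|---|---|---|
| 36.4°C | 54–59% | 97–100% | 90–100% |
| 36.6°C | 27–39% | 84–100% | 69–99% |
| 36.8°C | 8–27% | 55–100% | 34–98% |
| 37.0°C | 3–22% | 38–100% | 18–97% |

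At 36.6°C, 95 to 100% of flags come from the low limit. A 60-subject arm has 60 × 139 = 8,340 readings, of which about 2,300 to 3,200 would be flagged. Readings above 38.0°C are at most 0.07% of the total, or about 8,340 × 0.0007 ≈ 6. At 37.0°C the flags split about evenly between the low and high limits.

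**Chance rate for a count above 38.0°C.** Over 139 readings, the share of subjects with any reading above 38.0°C and no drug effect is about 0.1% at mean 36.6/SD 0.35, 6 to 18% at 36.8/0.45, and 15 to 41% at 37.0/0.45.

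**What a by-arm count could show.** Take 60 active and 30 placebo subjects, two-sided 0.05, normal approximation: power = Φ[(|p₁ − p₂| − 1.96·SE₀)/SE₁], with SE₀ from the pooled proportion and SE₁ from the separate ones. For assumed rates of 2% placebo and 15% active:

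- pooled proportion = (0.6 + 9)/90 = 0.1067
- SE₀ = √(0.1067 × 0.8933 × (1/30 + 1/60)) = 0.069
- SE₁ = √(0.02 × 0.98/30 + 0.15 × 0.85/60) = 0.053
- power ≈ 46%

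For 2% against 25% the same formula gives about 85%.

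**The case against.** The strongest reply is that the planned analysis of febrile reactions is the adverse event analysis, not the flag. The manual's tiers sit in a table of recommended adverse event actions, a blinded assessor watches each infusion, and events are recorded for the CRF. Reported fever and tachycardia are then counted by preferred term and arm in Table 14.3.1.2, by severity in 14.3.1.3 and by relationship in 14.3.1.4. This stands, and it limits the gap to measured excursions not reported as adverse events.

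A reader might infer that real fevers are buried. The documents do not support that: the listing prints each temperature with the asterisk in its own cell, Table 14.3.6.1.1 gives the maximum by visit and arm, and Figure 14.3.3.1 plots vital signs by visit and treatment. One qualification remains. SAP 9.3 mentions multiple timepoints only for seated blood pressure and does not say which of the 13 or more daily temperature readings enters the by-visit summary, so the tabulated maximum may miss the peak.

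A reader might also infer that the rule marks nearly everyone. No document gives a temperature mean, SD or measurement site, so that rests wholly on assumption.

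Lastly, Protocol 10.4.4 asks only that "Abnormal lab or vital sign values will be determined and flagged in the listings", which the SAP does. That is correct. By-arm counts go beyond the protocol's minimum, as the blood pressure table already does.

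**Conclusion.** The point holds in limited form. Three facts need no assumption: the temperature flag is listing-only, its limits differ from the manual's tiers, and no table counts subjects by arm for measured temperature or heart rate excursions. How often the flag would fire is assumption-dependent: about 84 to 100% of subjects at assumed means of 36.4 to 36.6°C, and about 38 to 100% at 36.8 to 37.0°C, taking 139 readings and no drug effect. The number of measured excursions that go unreported as adverse events cannot be estimated from the documents.

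The flag feeds no endpoint, test or halting rule, so the effect is confined to the display of secondary safety data. A reader might conclude that the low limit should go. The documents do not support that: Table 2 of the manual names low body temperature among the signs of anemia. No view is taken here on which temperature limit is clinically right.

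**What to change.** These are analysis changes only; no site action is altered.

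- Reconcile the temperature limits in SAP 9.3 and the Listing 16.2.8.2.1 footnote with the tiers in Appendix 11, or state why the two differ.
- Keep the existing listing asterisks, including the low-temperature mark.
- Add to Table 14.3.6.1.1, or to a new table parallel to 14.3.6.1.2, the number and percentage of subjects by arm with any post-first-dose temperature above 38.0°C, any at or above 39.0°C, and any heart rate above 100 bpm. Count each subject once per row, and state that all during-infusion and post-infusion readings are used.

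The cost is some SAP wording and a few table rows from data already collected. The rows will partly overlap the adverse event tables. Some chance excursions will appear in both arms, so the counts should be read as a comparison between arms, with the limited power shown above.

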5.4. Post-Infusion

- a. Upon completion of the infusion (~[REDACTED] post infusion start), monitor vital signs as follows:
 1. Collect seated BP, HR, RR, temp.
 2. Collect orthostatic BP: ask the subject to lie down; after 10 minutes, collect supine BP. Then, ask the subject to stand (provide assistance if needed); after 3 minutes, collect standing BP.
 3. Subject may return to a seated position.
 4. Approximately 17 minutes after collecting the subject's standing BP, next vitals (seated BP, HR, RR, temp.) should be recorded.
 5. Continue to monitor vital signs (seated BP, HR, RR, temp.) every 30 minutes (\pm 5 minutes) for 3.5 hours, such that vital signs are monitored every 30 minutes (\pm 5 minutes) for 4 hours after the end of infusion.
 6. After 4 hours post infusion, the subject may be discharged at the investigator's discretion.
- b. Educate the subject and the subject's trial partner regarding signs and symptoms to report to RN/Rx/MD such as: headache, nausea, fatigue, chills, myalgia, fever, shortness of breath, chest pain, back pain, hives, red or itchy skin, or itchy throat.
- c. The blinded Outcomes Assessor will ensure that the following information is documented in the subject's source record:
 - Any required labs are performed, reviewed by PI or physician designee; any abnormal values; and interpretation/decision.
 - All vital signs, including body weight, and orthostatic BP.
 - Any adverse reactions to the infusion and actions taken (refer to **Section 6: Monitoring for Adverse Reactions**).
- d. The PI or his/her designee will confirm the next infusion date with the subject and relay the request to the blinded Outcomes Assessor, unblinded Infusion Nurse, unblinded pharmacist, and other personnel as needed.

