Abbreviations: CRF = case report form; PT = preferred term; SOC = system organ class; TEAE = treatment emergent adverse event.
 Note: Percentages are n/Number of subjects in the Safety Set*100. Subjects are summarized by treatment received. AEs were coded using MedDRA version 21.0 A TEAE is any AE that occurs after the time of treatment with the study agent. This will include any AE with onset prior to time of treatment with study agent and increased severity after the treatment administration. Subjects are counted once for each SOC and once for each PT. Subjects are classified according to the closest relationship if the subject reported one or more events. Related TEAEs are those marked as Possibly Related or Definitely Related on the CRF. AEs with a missing relationship will be considered related for this summary. AEs are displayed by descending frequency of SOC, then PT within SOC, and then alphabetically by PT.
 SOURCE: Listing 16.2.7.1

Programming note: SOC & PT text should be in proper case in table, as shown in the shell. Ensure correct MedDRA version is printed in footnote.

Statistical Analysis Plan,
Sponsor Alkermes, Inc
Protocol Number ALK6021-201
PCN Number ALKA7951

Table 14.3.2.1
Incidence of Adverse Events Leading to Withdrawal by SOC, PT, and Treatment Safety Set

Same shell as Table 14.3.1.2

Programming note: AEs leading to withdrawal will be based on derived action taken in this table. The following should be added to Note: If the reason for discontinuation entered on the study completion CRF was "Adverse Event" and the AE occurred between the start of the first infusion in Period 1 through the final infusion in Period 2, the derived action taken was set to 'study drug withdrawn' regardless of what was indicated on the CRF since treatment is administered during two distinct periods and not on a continuous basis.

Table 14.3.2.2
Incidence of Serious Adverse Events by SOC, PT, and Treatment Safety Set

Same shell as Table 14.3.1.2

Programming note: Add SAE to abbreviations.

Table 14.3.2.3
Incidence of Adverse Events of Special Interest by SOC, PT, and Treatment Safety Set

Same shell as Table 14.3.1.2

Programming note: Add AESI to abbreviations.

Table 14.3.2.4
Incidence of Adverse Events with Terms Associated with Blood Pressure Changes by Infusion Period, SOC, PT, and Treatment Safety Set

Infusion Period System Organ Class Preferred Term	Placebo (N=XX) n (%)	GRF6021 (N=XX) n (%)	Overall (N=XX) n (%)
Any Occurrence			

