Sponsor Alkermes, Inc.
Protocol Number ALK6021-201
PCN Number ALKA7951

Table 14.3.6.1.1
Summary of Vital Signs by Study Visit and Treatment
Safety Set

(Same shell as Table 14.3.5.1.1; visits include Visit 1- Visit 19; parameters include Temperature (C), Respiration Rate (breaths per min), Sitting Systolic Blood Pressure (mmHg), Standing Systolic Blood Pressure (mmHg), and Supine Systolic Blood Pressure (mmHg), Heart Rate (bpm), Sitting Diastolic Blood Pressure (mmHg), Standing Diastolic Blood Pressure (mmHg), and Supine Diastolic Blood Pressure (mmHg), Weight (kg); SOURCE: Listing 16.2.8.2.)

Statistical Analysis Plan,
Sponsor Alkermes, Inc.
Protocol Number ALK6021-201
PCN Number ALKA7951

Table 14.3.6.1.2
Summary of Blood Pressures of Special Interest by Study Visit and Treatment Safety Set

Study Visit Category	Placebo (N=XX) n (%)	GRF6021 (N=XX) n (%)	Overall (N=XX) n (%)
Parameter: XXXXXXXXX			
Baseline [1]			
SBP > 180mmHg	XX (XX.X%)	XX (XX.X%)	XX (XX.X%)
SBP > 200 mmHg	XX (XX.X%)	XX (XX.X%)	XX (XX.X%)
SBP < 90 mmHg	XX (XX.X%)	XX (XX.X%)	XX (XX.X%)
Week 1 (Visit 3) 15 MIN DURING INFUSION			
SBP > 180mmHg	XX (XX.X%)	XX (XX.X%)	XX (XX.X%)
SBP > 200 mmHg	XX (XX.X%)	XX (XX.X%)	XX (XX.X%)
SBP < 90 mmHg	XX (XX.X%)	XX (XX.X%)	XX (XX.X%)
CFB ≥ 30%	XX (XX.X%)	XX (XX.X%)	XX (XX.X%)
Week 1 (Visit 3) 30 MIN DURING INFUSION			
SBP > 180mmHg	XX (XX.X%)	XX (XX.X%)	XX (XX.X%)
SBP > 200 mmHg	XX (XX.X%)	XX (XX.X%)	XX (XX.X%)
SBP < 90 mmHg	XX (XX.X%)	XX (XX.X%)	XX (XX.X%)
CFB ≥ 30%	XX (XX.X%)	XX (XX.X%)	XX (XX.X%)

Continue for other parameters. Sort alphabetically by parameter.

Abbreviations: CFB = change from baseline; DBP = diastolic blood pressure; SBP = systolic blood pressure.
 Note: Percentages are n/Number of subjects in the Safety Set*100. Subjects are summarized by treatment received. Blood pressures of special interest are as follows: seated systolic blood pressure > 180 mmHg, seated systolic blood pressure > 200 mmHg, seated systolic blood pressure < 90 mmHg, seated diastolic blood pressure >110 mmHg, seated diastolic blood pressure > 120 mmHg, seated diastolic blood pressure < 50 mmHg, or a change of ≥ 30% from baseline in seated systolic and/or seated diastolic blood pressure.
 [1] The baseline value for each variable is the value recorded prior to the first dose.
 SOURCE: Listing 16.2.8.1.3

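### Blood pressures of special interest are counted only within each visit and timepoint, so no planned table shows how many subjects per arm ever had one

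*SAP*

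**What the plan says.** SAP 9.3 defines BPSIs by cut-offs applied to seated readings: systolic above 180, above 200 or below 90 mmHg; diastolic above 110, above 120 or below 50 mmHg; or a change from baseline of at least 30% in either. They "will also be identified from the vital signs source data and summarized separately by study visit, timepoint, and treatment".

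One table carries this out: Table 14.3.6.1.2, "Summary of Blood Pressures of Special Interest by Study Visit and Treatment". After a baseline block, its shell shows "Week 1 (Visit 3) 15 MIN DURING INFUSION", then "Week 1 (Visit 3) 30 MIN DURING INFUSION", and continues in the same way. Each post-baseline block has three threshold rows and one row for a change of at least 30%. The footnote fixes the denominator: "Percentages are n/Number of subjects in the Safety Set*100". The programming note adds only the parameters and the diastolic cut-offs. The safety table list in SAP 13.3 contains no other BPSI table.

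The neighbouring Table 14.3.2.4, on adverse events with blood-pressure terms, is built differently. It opens with a block headed "Any Occurrence" and then separates events starting during and after each infusion period.

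**The concern.** Safety is the primary objective, and Protocol 2.3.1 names hypotension among the product's important identified risks. The direct question from the measured pressures is whether more subjects on GRF6021 than on placebo ever crossed a limit. Table 14.3.6.1.2 answers only whether they did so at, say, 30 minutes into the third infusion. With many readings per subject, most cells are likely to be small, and a reader cannot tell whether a scatter of ones and zeros is one subject flagged repeatedly or many subjects flagged once. These lead to very different safety conclusions.

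The table is also marked for the interim safety analysis (SAP 13.3). According to Protocol 10.4.7, that analysis informed removal of the inpatient requirement.

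**Working it through.** **1. The plan's own yardstick.** SAP 3.2 uses the rule of three for the active arm: 3/60 = 5.0%, which reproduces the stated figure of about 5% (exact one-sided: 1 − 0.05^(1/60) = 4.87%). It is a per-subject quantity. The documents give no count of BPSI blocks, so that is derived next.

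**2. Number of blocks per parameter.** Inputs:
- 10 infusions (Protocol 6.1.8).
- 1 seated reading before each infusion (Protocol Appendix 11, 5.3).
- *d* readings during infusion: at 15, 30, 45 and 60 minutes, then every 30 minutes (same section). The duration is redacted, so *d* is an assumption shown over a range; it counts readings strictly before the end.
- 1 reading at the end of infusion (Appendix 11, 5.4).
- 8 readings afterwards, "such that vital signs are monitored every 30 minutes" over 4 hours: the first at about 10 + 3 + 17 = 30 minutes, then 7 more over 3.5 hours.
- The Visit 3 pre-infusion reading is baseline (SAP 6.1.1), so subtract 1.
- 7 post-baseline visits without infusion (Visits 8, 9, 10, 16, 17, 18, 19).

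B = 10 × (1 + *d* + 1 + 8) − 1 + 7

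- Zero infusion time (absolute floor), *d* = 0: 10 × 10 + 6 = **106**
- 60 minutes, *d* = 3: 10 × 13 + 6 = **136**
- 120 minutes, *d* = 5: 10 × 15 + 6 = **156**
- 180 minutes, *d* = 7: 10 × 17 + 6 = **176**
- 240 minutes, *d* = 9: 10 × 19 + 6 = **196**

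With 2 parameters and 4 rows per block, that is 106 × 8 = 848 rows at the floor, and 1,088 to 1,568 rows for 60 to 240 minutes.

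**3. What the block counts reveal about subjects.** Let c_b be the number of subjects flagged in block b, and N the arm size. The number A of subjects ever flagged satisfies only

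max(c_b) ≤ A ≤ min(N, Σ c_b).

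With c_b = 1 in all 106 blocks and N = 60: 1 ≤ A ≤ min(60, 106) = 60, that is 1.7% to 100%. With N = 30 on placebo: 1/30 = 3.3% to 100%. Every block would print 1.7% against 3.3% across that whole range, so the arm comparison of per-subject incidence is undetermined.

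**4. Could another planned output supply it?**
- Table 14.3.6.1.1: summary statistics by visit. A minimum or maximum beyond a limit shows that someone crossed it, not how many did.
- Tables 14.3.2.3 (AESIs) and 14.3.2.4 (blood-pressure terms): per subject, but only for events recorded as AEs. Protocol 8.4.3 and SAP 10 leave that to the investigator.
- Listing 16.2.8.2.2: a BPSI flag for each subject's readings, with study visit and date but no timepoint column, and no totals.

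**The case against.** The strongest reply is that the information exists. Listing 16.2.8.2.2 carries the flag, SAP 13.4 sorts listings by treatment, site and subject, and anyone can count flagged subjects per arm. That is right, and a reader who infers that no planned output contains the answer goes too far. What is missing is the summary. A hand count from a listing is not a prespecified result, and as drawn the listing cannot separate readings during infusion from those after it.

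A reader might also infer from Protocol 8.4.3 that BPSIs are exactly the readings not called adverse events, so that the AE tables and Table 14.3.6.1.2 never overlap. SAP 9.3 does not support this. It selects readings by threshold from the source data without excluding AEs, and its limits differ from those in 8.4.3 (for example, a change of at least 30% against more than 25%). The narrower statement stands: the AE and AESI tables miss threshold readings that were not judged to be AEs.

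It is also fair to say that BPSI incidence is not a named endpoint; the secondary safety endpoint is change from baseline in vital signs. That limits the weight of the point. It does not explain why the AE counterpart has subject-level rows and this table has none.

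**Conclusion.** The concern holds as a gap in tabulation, worth correcting but not a threat to the trial's validity. No planned table gives the number of subjects per arm with at least one BPSI, and it cannot be recovered from 106 or more blocks per parameter.

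The block count assumes one block per scheduled seated reading under protocol v5.0. Subjects dosed under earlier versions, with 2 rather than 4 hours of post-infusion monitoring, have fewer readings. The conclusion does not depend on the redacted infusion duration. The 1/60 to 60/60 range is a logical bound, not a forecast: readings taken minutes apart in one person are related, and the documents give no correlation from which to estimate where the true figure would lie.

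**What to change.** Open Table 14.3.6.1.2 with subject-level rows that count each subject once, mirroring the first block of Table 14.3.2.4:

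- n (%) with at least one post-baseline BPSI of any kind, and by criterion, overall and by dosing period.
- Changes of at least 30% split into falls and rises. As drawn, the row pools both directions, so it cannot speak to hypotension.
- As denominator, subjects with at least one post-baseline seated reading in that period. The shell divides by the whole Safety Set, whereas SAP 4.1 bases by-visit displays on subjects with non-missing data.
- For the overall rows, the GRF6021 minus placebo difference with a 95% Wilson interval, as Table 14.3.1.1 already does for TEAEs and SAEs.

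Amend SAP 9.3 to match and keep the timepoint rows as supporting detail. While the shell is open, correct its source line, which cites the urinalysis listing (16.2.8.1.3) instead of the blood pressure listing (16.2.8.2.2).

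Cost: 5 criteria for each of 2 parameters plus one any-BPSI row is 11 rows; overall and two dosing periods make 33, beside at least 848 timepoint rows. The dataset is the same, and no assessment or clinical rule changes.
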